### **Peripheral blood:**

1. Chimerism analysis: Using single-nucleotide polymorphisms, relative contributions from donor vs. recipient in sorted CD3+ and CD33+ cells will be measured and expressed as a percentage.
2. Immune reconstitution: [name] has developed a panel called the Immunome to study reconstitution of T cells, NK cells and B cells post-transplant. Specific information regarding stages of activation of T cells is also available from this panel.
3. Immune response post Daratumumab: The Immunome panel will be performed at the following time points: Day 90, 180 and 365 (+/- 7days).

Date of protocol: 10/14/2020

IRB Approval Date: 11/24/2020

Version of protocol: 7

IND number: 139015

Institutional protocol number: OSU 17102

4. Phenotypic studies to evaluate T-cell exhaustion will be performed on bone marrow samples pre-and post-treatment with Daratumumab
5. Phenotypic studies to evaluate activation status of NK-cells will be performed on bone marrow samples pre-and post-treatment with Daratumumab
6. Measurements of cytokines including but not limited to IFN-  $\gamma$  will be measured at relapse, pre and post Daratumumab treatment.
7. Exosomes from bone marrow will be examined at these serial times for both number and also content (protein, mRNA, and miRNAs).
8. CD38, CD55, and CD59 expression in circulating blood cells will be evaluated
9. Three tubes of blood will be collected at each time point for correlative studies.

## 7 STUDY DESIGN

### 7.1 OVERVIEW OF STUDY DESIGN

This is a phase I/II study that evaluates combination of Daratumumab and escalating doses of donor lymphocyte infusions. Donor lymphocyte infusions will be given within 72 hrs. of daratumumab dose. The following dose levels are used.

1. Phase I study with the following dose levels for related sibling donors:
  - a. Dose level 1: Dara 16mg/kg
  - b. Dose level 2: Dara 16mg/kg + DLI (1 infusion at any time between weeks 3-5) : 1x10e6 CD3/kg
  - c. Dose level 3: Dara 16mg/kg + DLI (1 infusion at any time between weeks 3-5): 1x10e7 CD3/kg
2. Phase I study with the following dose levels for unrelated donors:
  - c. Dose level 1: Dara 16mg/kg
  - d. Dose level 2: Dara 16mg/kg + DLI (1 infusion at any time between weeks 3-5): 1x10e5 CD3/kg
  - e. Dose level 3: Dara 16mg/kg + DLI (1 infusion at any time between weeks 3-5): 1x10e6 CD3/kg
3. Phase I study with the following dose levels for haploidentical donors:
  - f. Dose level 1: Dara 16mg/kg
  - g. Dose level 2: Dara 16mg/kg + DLI (1 infusion at any time between weeks 3-5): 1x10e4 CD3/kg
  - h. Dose level 3: Dara 16mg/kg + DLI (1 infusion at any time between weeks 3-5): 1x10e5 CD3/kg

Patients with MRD will not be enrolled until the DLT period for dose level 1 has been completed and it has been determined that the treatment schedule is safe. Patients must be positive for MRD disease as

Date of protocol: 10/14/2020

IRB Approval Date: 11/24/2020

Version of protocol: 7

IND number: 139015

Institutional protocol number: OSU 17102

[figure not shown]
determined by the combined analyses of flow cytometry, genomic sequencing and cytogenetics. Patients who do not demonstrate evidence of MRD in all three methods will not be eligible for the trial.

Bone marrow biopsies are done at the completion of 8 weeks. The maximal tolerated dose of DLI is chosen for expansion to the phase II portion of the study.

If patients are found to be in CR at the end of 8 weeks and treating physician concludes that patient continues to benefit from treatment, patients may proceed to Daratumumab maintenance with a schedule of 16mg/kg every 2 weeks for 16 weeks (8 doses) and then monthly for 6 months .

For patients with rapidly progressive disease despite 4 doses of Daratumumab, they will come off trial.

The dose level that is deemed safe will be chosen for the phase II portion of the study.

Dose level	Sibling donor	Unrelated donor	Haploidentical donor
Dose level 1	Dara 16mg/kg	Dara 16mg/kg	Dara 16mg/kg
Dose level 2	Dara 16mg/kg + DLI at weeks 3-5: 1x10e6 CD3/kg	Dara 16mg/kg + DLI at weeks 3-5: 1x10e5 CD3/kg	Dara 16mg/kg + DLI at weeks 3-5: 1x10e4 CD3/kg
Dose level 3	Dara 16mg/kg + DLI at weeks 3-5: 1x10e7 CD3/kg	Dara 16mg/kg + DLI at weeks 3-5: 1x10e6 CD3/kg	Dara 16mg/kg + DLI at weeks 3-5: 1x10e5 CD3/kg

## 7.2 NUMBER OF PATIENTS

For phase I, we expect to enroll a minimum of 3 and a maximum of 18 patients for the related donor portion and 3-18 patients for the unrelated donor cohort. Accounting for 10% unevaluable for DLT, we expect 4-20 patients for each cohort in summary we expect 8-40 patients for phase I portion of the study. Enrollment can occur in parallel for both related and unrelated donor arms of the study. For Phase II, we will expect to enroll 25 patients.

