## 16 STATISTICAL CONSIDERATIONS

Study design/Sample size

This is a phase I/II study evaluating the combination of Daratumumab and escalating doses of DLI in patients with relapsed AML or transformed from MDS to AML post allo-HCT. Three dose levels will be used for related sibling donors and unrelated donors respectively.

Study Design: The standard 3+3 design will be applied to determine MTD of donor lymphocyte infusion when given with a fixed dose of Daratumumab. The dose escalation process for related sibling donor and unrelated donor will be conducted concurrently, but separately.

Dose escalation will proceed within each cohort according to the following scheme.

Number of Subjects with DLT at a Given Dose Level	Escalation Decision Rule
0 out of 3	Enter 3 subjects at the next dose level.
1 out of 3	
Enter 3 more subjects at this dose level.
 

• If 0 of these 3 subjects experience DLT, proceed to the next dose level.

• If 1 or more of this group suffer DLT, then dose escalation is stopped, and this dose is declared the maximally administered dose. Three (3)

Date of protocol: 10/14/2020

IRB Approval Date: 11/24/2020

Version of protocol: 7

IND number: 139015

Institutional protocol number: OSU 17102

	additional subjects will be entered at the next lowest dose level if only 3 subjects were treated previously at that dose.
>2	Dose escalation will be stopped. This dose level will be declared the maximally administered dose (highest dose administered). Three (3) additional subjects will be entered at the next lowest dose level if only 3 subjects were treated previously at that dose.
<1 out of 6 at highest dose level below the maximally administered dose	This is generally the recommended maximally tolerated dose.

The MTD will be defined as the highest safely tolerated dose where at most one patient in six experiences DLT during DLT observation period. The DLT observation period is defined as below.

Dose Level	DLT observation period
1	From the first dose of Daratumumab till 7 days post 3 rd dose
2/3	From the first dose of Daratumumab till at least 4 weeks post DLI

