If a patient in dose level 1 receives less than 3 doses of Daratumumab due to reasons other than toxicity, then this patient will not be evaluable for DLT and will be replaced. An additional patient will be added to the dose cohort. For dose level 2 or 3, if a patient does not receive 3 doses of Daratumumab and DLI due to reasons other than toxicity, then this patient will not be evaluable and will be replaced. There will be no intrapatient dose escalation. Phase I may involve as few as 3 patients (three at the starting dose level if  $\geq 2$  DLTs are experienced) and a maximum of 18 patients will be treated, six at each of the 3 dose levels. We assume that 10% of the patients in this group will not be evaluable due to not finishing the DLT observation period. So we expect to accrue a minimum of 4 patients and a maximum of 20 patients.

At OSU, 125 patients with AML/MDS underwent allo-HSCT in 2012 and 2013. Among these, 32 patients relapsed. About 40% were from related donor and 60% from unrelated donor. So we expect to accrue approximately 6 patients for the related sibling donor cohort and 10 patients for the unrelated donor cohort per year. Hence, the minimum study duration for phase I would be about 8-10 months and the maximum study duration would be around 2.5-3.5 years (accounting for the DLT observation period) for related sibling donors and unrelated donors respectively.

After the MTD has been established, we will expand to Phase II trial. For phase II part, considering that patients receiving transplant from related sibling donor or unrelated donor with each treated at the corresponding MTD of Daratumumab plus DLI are expected to have similar profiles for response and toxicities, we will combine these 2 cohorts together in phase II stage. The null hypothesis is that combination of Daratumumab and DLI has a response rate of < 10% in patients with relapsed AML following allo-HSCT. The alternative hypothesis is that Daratumumab has a response rate of at least 30% in patients with relapsed AML following allo-HSCT. With a type 1 error (alpha): 0.05, and a type 2 error (beta = 1 – power): 0.20, the sample size would be 25 patients for Phase II. If the number of patients achieving ORR is 6 or more, then we reject the null hypothesis. We would include 3-6 patients from

Date of protocol: 10/14/2020

IRB Approval Date: 11/24/2020

Version of protocol: 7

IND number: 139015

Institutional protocol number: OSU 17102

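### The stated Phase I size of 8–40 leaves out the haploidentical ladder; on the plan's own convention three donor cohorts give 12–60

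*Combined protocol and SAP*

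**What the plan says.** **The ladders.** Section 7.1 contains the entry "Phase I study with the following dose levels for haploidentical donors", followed by daratumumab alone and then two DLI levels. At each DLI level the haploidentical cell dose differs from both the sibling and the unrelated dose. The synopsis (Study Design) and the dose table in section 7.1 repeat this third ladder, and the synopsis lists all three ladders under a single 3+3 heading. The inclusion criteria in the synopsis and in section 8.1 admit haploidentical recipients.

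**The size.** Section 7.2 counts a related and an unrelated cohort of 3 to 18 each, raises each to 4 to 20 for 10% unevaluable, and concludes: "in summary we expect 8-40 patients for phase I portion of the study". The synopsis gives the same total. Section 16 explains the 18: "a maximum of 18 patients will be treated, six at each of the 3 dose levels".

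**Escalation, accrual and duration.** Section 16 states: "Three dose levels will be used for related sibling donors and unrelated donors respectively", and "The dose escalation process for related sibling donor and unrelated donor will be conducted concurrently, but separately". On accrual: "we expect to accrue approximately 6 patients for the related sibling donor cohort and 10 patients for the unrelated donor cohort per year". Section 7.3 gives one duration for the related arm and one for the unrelated arm.

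**Phase II.** After naming related sibling and unrelated donors, section 16 says "we will combine these 2 cohorts together in phase II stage". Section 7.1 carries the dose forward without mentioning donor type: "The maximal tolerated dose of DLI is chosen for expansion to the phase II portion of the study".

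**The concern.** The design sections enrol three donor cohorts, while the statistical section sizes, escalates and accrues two. A third 3+3 ladder adds patients and time, so the stated Phase I maximum should not be the same with it as without it.

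Two things are at stake. The Phase I number that the trial has put forward is too small for the design it describes. The timeline also has no component for a cohort that may be slow to fill. A smaller matter is that a reader has to infer from section 16 how haploidentical patients are treated in Phase II.

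**Working it through.** **Inputs.** 3 to 18 evaluable per cohort, with 18 = 6 × 3 levels (sections 7.2 and 16); 10% unevaluable (sections 7.2 and 16); separate escalation by donor type (section 16); three ladders (synopsis, section 7.1).

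**Formula.** Enrolled per cohort = evaluable / (1 − 0.10), rounded up.

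1. *Reproduce the plan's figure.* Minimum: 3 / 0.9 = 3.3, so 4. Maximum: 18 / 0.9 = 20. Two cohorts: 2 × 4 = 8 and 2 × 20 = 40. This is exactly the stated 8–40.

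2. *Check how 40 counts dose level 1.* If the two cohorts shared one dose level 1, the maximum would be 6 + 2 × 12 = 30 evaluable, and 30 / 0.9 = 33.3, so 34. The stated 40 therefore counts dose level 1 once in each cohort.

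3. *Same convention, three cohorts.* Minimum: 3 × 4 = 12. Maximum: 3 × 18 = 54 evaluable, and 54 / 0.9 = 60, which is 20 above the stated 40.

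4. *Conditional case: one dose level 1 for all donor types.* Maximum: 6 + 3 × 12 = 42 evaluable, and 42 / 0.9 = 46.7, so 47 (49 if the allowance is rounded up block by block: 7 + 3 × 14). Minimum: 3 / 0.9, so 4, if the shared level stops the trial. Even without the 10% allowance, 42 is more than 40.

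| Reading | Evaluable maximum | Enrolled range |
|---|---|---|
| As stated, two cohorts | 36 | 8–40 |
| Three cohorts, plan's convention | 54 | 12–60 |
| Three cohorts, dose level 1 shared (not stated in the plan) | 42 | 4–47 |

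5. *Can the maximum be reached?* Yes. Under the section 16 scheme, one DLT in the first three patients and none in the next three uses six patients and still escalates.

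6. *Accrual and duration.* Section 16 reports 32 relapses over two years, or 16 per year. Its 40% and 60% shares give 6.4 and 9.6, stated as 6 and 10, so no share is left for haploidentical donors. For 20 patients, 20 / 6 = 3.3 years (stated maximum 3.5) and 20 / 10 = 2.0 years (stated maximum 2.5). The stated maxima say that they allow for DLT observation. The gaps of about 2 and 6 months are unequal, so this is only a rough match, but it is a match to two cohorts.

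7. *Haploidentical duration.* The documents give no rate. Assuming 2 to 6 patients per year, 20 patients take 20 / 2 = 10 years down to 20 / 6 = 3.3 years, before DLT observation.

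**The case against.** **Related donor may include haploidentical donors.** Sections 7.2 and 7.3 say related, not sibling. If dose levels were ordinal with donor-specific cell doses, one related cohort of 18 would bring the total back to 40. This does not stand. Section 16 calls the cohort related sibling, its 18 is six at each of three levels, and the haploidentical DLI levels differ from the sibling levels. One 18-patient sequence cannot establish an MTD on both.

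**No escalation rule covers the haploidentical ladder.** A reader might infer this from section 16, but it goes too far. The synopsis puts all three ladders under the 3+3 design, and the section 16 table applies within each cohort. What is missing is the cohort's name in section 16, not the rule.

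**Haploidentical patients enter only dose levels 2 and 3.** The eligibility wording might suggest this, which would give 18 + 18 + 12 = 48 evaluable and 54 enrolled. But the synopsis, section 7.1 and the dose table all give these donors a dose level 1. The qualifier in section 8.1 can equally apply to the whole transplant criterion, since another item waives prior transplant at dose level 1. The 54 should not be used.

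**Forty is a ceiling that would halt enrolment.** The documents do not say so; section 7.2 gives an expected number.

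**The Phase II population is undefined.** Section 16 names the two pooled cohorts, and a general evaluability rule in section 16.2 need not repeat donor type. This objection stands: the Phase II matter is a clarification, not a flaw in the test.

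**A third arm need not lengthen Phase I.** Section 7.2 lets the two counted arms enrol in parallel. If the third did too, its full 20 patients would outlast the sibling arm's 20 only at fewer than that arm's 6 per year. That is fair, but the plan gives no rate from which to judge.

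**Conclusion.** The point holds. The Phase I size, durations, accrual and section 16 escalation text cover two donor cohorts, while the protocol enrols three. On the plan's convention the range is 12–60 instead of 8–40. It rests on three inputs from the plan: separate escalation for each donor type, 3 to 18 evaluable per cohort, and 10% unevaluable. The minimum of 12 also follows the plan in rounding up cohort by cohort.

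The 60 is a worst case needing six patients at every level of all three ladders; it is not a forecast. The 47 depends on a shared dose level 1, which no section states. It is plausible because that level is the same treatment for every donor type and admits patients with no prior transplant. Either way the maximum exceeds 40, by 20 or by 7.

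The added duration cannot be derived from the documents; the 3.3 to 10 years shown rests on an assumed rate. The Phase II rule of 6 or more responders in 25 does not change.

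**What to change.** 1. Restate the Phase I size in the synopsis and section 7.2 as 12–60, or as 4–47 if dose level 1 is declared shared across donor types. Say which applies.
2. Name the haploidentical cohort in the section 16 text on dose levels, escalation and size.
3. Add its assumed accrual rate and duration to sections 7.3 and 16, and say whether the present 16 per year already includes such patients.
4. Add one sentence, settled before Phase II responses are seen, confirming how haploidentical patients are handled in Phase II. Reconcile the synopsis (Study Design) and sections 7.1, 16 and 16.2 with it.

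The cost is wording in four places, a restated range, and one accrual assumption with its duration. No dose, escalation rule or Phase II decision rule has to change.

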### 7.3 DURATION OF STUDY

For phase I related donor arm, we expect the study duration between 10 months to 3.5 years including DLT observation period, while for the unrelated donor arm, it will take about 8 months to 2.5 years. For phase II, the study duration will be around 2 years including following up period.

## 8 STUDY POPULATION

### 8.1 INCLUSION CRITERIA

1. Age  $\geq$  18 years
2. AML or MDS relapse following Allo-HSCT (Morphological relapse, or MRD positive by flow cytometry, cytogenetics, and molecular mutations)
3. Patients who received a 10/10 HLA-matched allogeneic HCT either from sibling donors or unrelated donors or at least a 5/10 haploidentical transplant for Dose level 2 and 3
4. Patients with R/R AML must not be candidates for available therapies known to be effective for treatment of their AML.
5. For patients in Dose level 1 (Daratumumab only), relapsed refractory AML patients who have previously not received an allogeneic HCT are eligible.
6. Engraftment must have occurred as defined by platelet (PLT) count  $> 20,000/\mu\text{L}$  and ANC  $\geq 0.5$
7. ECOG performance status  $< 3$
8. Creatinine clearance  $> 40 \text{ ml/min}$  (Calculated or measured)
9. Aspartate aminotransferase (AST)  $< 3 \times$  upper limit of normal (ULN), alanine aminotransferase (ALT)  $< 3 \times$  ULN, and total bilirubin  $< 1.5 \times$  ULN
10. Off calcineurin inhibitors for at least 2 weeks
11. Prednisone dose  $\leq 20 \text{ mg/day}$ .
12. Patients with proliferative disease can be cytoreduced with cytotoxic chemotherapy at investigator's discretion, but there should be at least a 14 day window between start of cytoreductive therapy and start of Daratumumab
13. Blast count  $< 20 \text{ K/day}$  (hydrea use is allowed)
14. Patient willing to agree to study-related research marrows
15. Female patients of childbearing potential who are sexually active must be willing to use an effective barrier method of birth control to avoid pregnancy during the study and for a minimum of 3 months after stopping study treatment
16. Male patients with partners of childbearing potential who are sexually active must be willing to use an effective barrier method of birth control to avoid pregnancy during the study and for a minimum of 3 months after stopping study treatment

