### 8.2 EXCLUSION CRITERIA

1. No demonstrable evidence of donor chimerism ( $< 55$  donor CD3 or CD33 chimerism)
2. Patients with a molecular mutation without chromosomal abnormalities or declining chimerisms (MRD status must be verified by surface marker and mutational analyses)
3. Active graft-versus-host disease (GVHD) grades I-IV; prior acute GVHD could have occurred but resolved at time of initiation of Daratumumab
4. Extensive chronic GVHD requiring ongoing immunosuppression with calcineurin inhibitors or more than 20 mg of prednisone
5. Patients with FLT3+ AML or blast crisis CML who have not yet received post-transplant TKI therapy

6. Active CNS or testicular disease
7. Subject is:
  - 7.2 seropositive for human immunodeficiency virus (HIV)
  - 7.3 seropositive for hepatitis B (defined by a positive test for hepatitis B surface antigen [HBsAg]).  
Subjects with resolved infection (ie, subjects who are HBsAg negative but positive for antibodies to hepatitis B core antigen [anti-HBc] and/or antibodies to hepatitis B surface antigen [anti-HBs]) must be screened using real-time polymerase chain reaction (PCR) measurement of hepatitis B virus (HBV) DNA levels. Those who are PCR positive will be excluded. EXCEPTION: Subjects with serologic findings suggestive of HBV vaccination (anti-HBs positivity as the only serologic marker) AND a known history of prior HBV vaccination, do not need to be tested for HBV DNA by PCR.
8. seropositive for hepatitis C (except in the setting of a sustained virologic response [SVR], defined as aviremia at least 12 weeks after completion of antiviral therapy).
9. Patients must not have chronic obstructive pulmonary disease with a forced expiratory volume in 1 second (FEV1) < 50% of predicted normal. FEV1 is required for patients suspected of having chronic obstructive pulmonary disease and are not eligible if FEV1 is < 50% of predicted normal.
10. Patients must not have moderate or severe persistent asthma within the past 2 years and must not have currently uncontrolled asthma of any classification.
11. Active autoimmune disease prior to transplant
12. Female patients of childbearing potential who are sexually active and unwilling to use an effective barrier method of birth control to avoid pregnancy during the study and for a minimum of 3 months after study treatment.

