## 17 QUALITY CONTROL AND QUALITY ASSURANCE

### Protocol Deviations

The investigator should not deviate from the protocol, except where necessary to eliminate an immediate hazard to study subjects. Should other unexpected circumstances arise that will require deviation from protocol-specified procedures, the investigator should consult with the sponsor or designee (and IRB or IEC, as required) to determine the appropriate course of action. There will be no exemptions (a

Date of protocol: 10/14/2020

IRB Approval Date: 11/24/2020

Version of protocol: 7

IND number: 139015

Institutional protocol number: OSU 17102

prospectively approved deviation) from the inclusion or exclusion criteria. The site should document all protocol deviations in the subject's source documents. In the event of a significant deviation, the site should notify the IRB. Significant deviations include, but are not limited to, those that involve fraud or misconduct, increase the health risk to the subject, or confound interpretation of primary study assessment. A Protocol Deviation Form should be completed by the sponsor or designee for any significant deviation from the protocol.

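### Never-transplanted patients are admitted at dose level 1 but removed by the donor-chimerism exclusion, and no rule says whether they count toward clearing a level whose lead DLT they cannot develop

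*Combined protocol and SAP*

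**What the plan says.** **Eligibility.** Section 8.1 item 5 (synopsis inclusion item 3) provides that, at dose level 1, "relapsed refractory AML patients who have previously not received an allogeneic HCT are eligible". The general disease criterion, item 2, is "AML or MDS relapse following Allo-HSCT". Item 6 reads "Engraftment must have occurred as defined by platelet (PLT) count" and continues with platelet and neutrophil thresholds. Section 8.2 item 1 (synopsis exclusion item 1) excludes patients with "No demonstrable evidence of donor chimerism", set at below 55% donor CD3 or CD33. Neither item 6 nor this exclusion is limited by dose level, whereas the HLA-match criterion (8.1 item 3) is expressly confined to levels 2 and 3. On waivers, Section 17 says "There will be no exemptions".

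**Escalation.** Section 16 states: "The dose escalation process for related sibling donor and unrelated donor will be conducted concurrently, but separately". Section 7.1 lists the dose levels only by donor type. Section 5.1 sets the phase I objective as the MTD in post-transplant patients.

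**DLT and evaluability.** Section 9.6 puts grade 3-4 GVHD first among the DLTs. It also counts daratumumab-related grade 3-4 non-hematologic toxicity and unresolved grade 4 hematologic toxicity. The synopsis enrollment schedule makes leaving level 1 depend on seeing neither infusional toxicity nor GVHD. The synopsis and Section 16 decide DLT evaluability at level 1 by whether three daratumumab doses were received. Transplant history plays no part.

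**The concern.** Two problems follow from the same carve-out.

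First, the criteria contradict each other. A never-transplanted patient has no donor cells, so one criterion admits the patient and another always excludes the patient. Section 16.2 builds the efficacy and safety datasets from eligible patients, so their place in the analysis sets is also unclear.

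Second, the escalation rule does not say what to do with them. They have no donor, so no cohort is theirs. Yet nothing makes them unevaluable for DLT and nothing limits their number. With no graft, and no DLI at level 1, they cannot develop GVHD. If they are counted among the three or six patients who clear level 1, that clearance carries less information, or none, on GVHD in the population named in the objective. Level 1 also controls more than the first DLI level: Section 7.1 holds back MRD patients until its DLT period is complete and the schedule is judged safe.

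**Working it through.** **The plan's nearest figures.** The plan gives no probability of clearing level 1. Its phase I size per cohort does reproduce: 3 to 18 evaluable with 10% unevaluable gives 3/0.9 = 3.3, rounded up to 4, and 18/0.9 = 20, as in Sections 7.2 and 16.

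**The passages side by side, for a never-transplanted patient at level 1**

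| Text | Result |
|---|---|
| 8.1 item 5 | Admitted |
| 8.1 item 2 | Not met, but item 5 reads as an express exception to it |
| 8.1 item 6 | Wording presupposes a graft; the count thresholds can be met |
| 8.2 item 1 | Always excluded; no exception written |
| Section 17 | No case-by-case waiver of 8.2 item 1 |
| Section 16, escalation | No cohort assigned |
| Synopsis and Section 16, evaluability | Evaluable after three daratumumab doses |

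**Effect on clearing level 1.** Section 16 escalates after 0 of 3 DLTs, or after 1 of 3 followed by 0 of 3. Inputs:

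- *g*: the grade 3-4 GVHD probability at level 1 in a post-transplant patient. The documents give none, so 10% to 50% is an assumed range.
- Never-transplanted patients: GVHD probability 0.
- *k*: the number of never-transplanted patients in each group of three (same mix in both groups), with *j* = 3 − *k*.
- Other DLTs: set to 0 at first.

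P(clear) = A + B × A, where A = (1 − g)^j and B = j × g × (1 − g)^(j − 1).

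At g = 0.30:

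- k = 0: 0.343 + 0.441 × 0.343 = 0.494
- k = 1: 0.490 + 0.420 × 0.490 = 0.696
- k = 2: 0.700 + 0.300 × 0.700 = 0.910
- k = 3: 1.000

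| Assumed g | k = 0 | k = 1 | k = 2 | k = 3 |
|---|---|---|---|---|
| 10% | 0.906 | 0.956 | 0.990 | 1.000 |
| 20% | 0.709 | 0.845 | 0.960 | 1.000 |
| 30% | 0.494 | 0.696 | 0.910 | 1.000 |
| 40% | 0.309 | 0.533 | 0.840 | 1.000 |
| 50% | 0.172 | 0.375 | 0.750 | 1.000 |

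**Sensitivity.** Give every patient an assumed 10% risk of another DLT, independent of GVHD, with g = 30%. A post-transplant patient's DLT risk is then 1 − 0.9 × 0.7 = 0.37. P(clear) is 0.360, 0.521, 0.721 and 0.906 for k = 0, 1, 2 and 3. The level is lower but the pattern is the same.

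**The case against.** The other side has several good points.

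- **Item 5 is a deliberate exception.** It is limited to level 1 and reads naturally as overriding item 2. Section 17 bars waivers; it does not cancel an exception written into the criteria. This stands for item 2. It does not help with the chimerism exclusion, for which no exception is written.
- **Engraftment.** A reader might infer that these patients also fail item 6. The documents do not support that firmly, because the definition rests on counts that such patients can reach. Only the wording needs clarifying.
- **Counting.** A reader might infer that these patients do open the DLI levels. Section 16 escalates within each cohort and gives them none, so the documents are silent. They could count; it is not established that they do.
- **Level 1 tests more than GVHD.** These patients do inform infusional toxicity and the daratumumab-related non-hematologic and unresolved grade 4 hematologic DLTs.
- **Later safeguards.** The DLT window at levels 2 and 3 starts with the first daratumumab dose, before DLI, in transplanted patients. Section 12.1.1 has GVHD assessed before every dose, Section 9.4 bars dosing during active GVHD, and Section 9.6 puts enrollment on hold after one grade 3-4 case. So it would be wrong to infer that GVHD on daratumumab alone would go unobserved.

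These points narrow the consequence. They leave the conflict between the two criteria and the missing counting rule untouched.

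**Conclusion.** The point holds in this form: Section 8.1 item 5 and Section 8.2 item 1 cannot both be followed, and the plan does not say where never-transplanted patients belong or whether they count in the level 1 decision. If they count, the level 1 test for GVHD is weaker. At an assumed 30% rate with no other DLTs, one such patient in each group of three raises the chance of clearing level 1 from 0.494 to 0.696, and two raise it to 0.910. With three, clearance says nothing about GVHD at any rate.

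These figures rest on assumed GVHD rates, independent patients and the same mix in both groups of three. They show what could happen; the number of such patients who enrol is unknown and uncapped.

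A reader might also infer that these patients will distort the phase II response rate. Section 16 carries forward only phase I patients treated at the MTD, so this arises only if level 1 becomes the MTD.

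**What to change.** 1. In Section 8 and the synopsis, reconcile item 5 of 8.1 with item 1 of 8.2 by stating which transplant-dependent criteria apply only to post-transplant patients. Clarify the wording of 8.1 items 2 and 6 at the same time. Which patients to admit is for the sponsor to decide.
2. In Section 16, state that clearance of level 1 in each donor cohort is based on DLT-evaluable post-transplant patients.
3. Report never-transplanted patients separately. If level 1 becomes the MTD, keep them out of the phase II ORR.

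The cost is a few sentences in an amendment and possibly slower accrual at level 1. The plan's own timeline should absorb this. Section 16 derives accrual from 32 post-transplant relapses over two years, which is 16 a year: 16 × 0.4 = 6.4 related and 16 × 0.6 = 9.6 unrelated, matching its stated 6 and 10. That projection does not rely on never-transplanted patients, so what is given up is any speed gained by counting them.
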